11.2.7. Inferential Analysis of Pharmacokinetic Data

The PK parameters (Cmax, AUCinf and AUClast) of verinurad, M1, M8, allopurinol and oxypurinol will be analysed using an analysis of variance model following a natural logarithmic transformation, with fixed effects for treatment and subject. Least-squares geometric means, 2-sided 95% confidence intervals, ratios of geometric means together with 2-sided 90% confidence intervals of test treatment (verinurad+allopurinol+cyclosporine or verinurad+allopurinol+rifampicin), and reference treatment (verinurad+allopurinol) will be estimated and presented. Descriptive statistics will be presented for PK concentration-time data and PK parameters for verinurad, M1, M8, allopurinol and oxypurinol.

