10.2. Pharmacokinetic Variables

Where possible, the following PK parameters will be determined for verinurad, its metabolites M1 and M8, allopurinol and oxypurinol using plasma concentrations for Treatment Period 1 (reference treatment), Treatment Period 2 (test treatment 1) and Treatment Period 3 (test treatment 2).

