11.1.3. Pharmacokinetic Analysis Set

The PK analysis set will include all subjects in the Safety Analysis Set who receive verinurad+allopurinol dose and who have at least 1 quantifiable post-dose plasma concentration. In case of an important protocol deviation or event, affected PK data will be excluded from the descriptive and inferential statistical analyses, but will still be included in the study result listings.

Data for a subject may be excluded from the descriptive and inferential statistical analyses as a result of the following:

- Where a subject experienced vomiting at or before median tmax.
- Where the pre-dose concentration for an analyte is > 5% of Cmax in a specific PK sampling period

The exclusion of any subjects or time points from the calculation of the PK parameters will be documented by the PK Scientist including the reason(s) for exclusion.

The available concentration data and PK parameter data for any subjects excluded from the PK analysis set will be listed only. Concentration data for subjects excluded from the PK analysis set will be presented in the individual figures of concentration versus time plots.

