11.4. Determination of Sample Size

The number of subjects is based on the desire to gain adequate information on the primary endpoints while exposing as few subjects as possible to study procedures. Interpretation of the results will be based on the size of the treatment ratio and associated 90% CI. It is estimated that 12 subjects will provide a CI within 1.58 to 2.53 with a probability of 80% if the calculated treatment ratio is 2. This is based on an intra-subject CV of 24% for verinurad.

A total of 14 healthy subjects will be enrolled to ensure at least 12 evaluable subjects at the end of the last treatment period.

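### The 95% CIs for each treatment's geometric mean leave out between-subject variance and are too narrow for the population mean; the primary ratios and their 90% CIs are unaffected

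*Combined protocol and SAP*

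**What the plan says.** Protocol Section 11.2.7 analyses Cmax, AUCinf and AUClast of five analytes by a log-scale ANOVA "with fixed effects for treatment and subject. Least-squares geometric means, 2-sided 95% confidence intervals". From that model it then lists "ratios of geometric means together with 2-sided 90% confidence intervals of test treatment" against the reference. The synopsis repeats this. No other model or source is named for the 95% intervals. Section 11.2.1 says that no separate SAP will be written, so this text is the working specification.

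The primary outcome measures (Table 2-1) are ratios, and Section 11.4 states: "Interpretation of the results will be based on the size of the treatment ratio and associated 90% CI". The only variability figure is in the same section: "This is based on an intra-subject CV of 24% for verinurad". No between-subject CV is given for any analyte.

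**The concern.** Every subject receives all three treatments. A fixed subject effect removes between-subject differences from the residual, which is what the ratio needs. It removes them from the standard error of each treatment mean as well, and there they belong if the interval is to describe the population from which the subjects were drawn.

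The intervals are a prespecified output for five analytes and three parameters, shown beside the ratios. Describing PK on each treatment is a secondary objective (Table 2-2). A reader who took one of these intervals as the uncertainty of exposure on that treatment would see too much precision. No objective or decision in the protocol rests on them.

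**Working it through.** **Inputs.** Intra-subject CV 24% and n = 12 evaluable of 14 enrolled (Section 11.4); three periods, all subjects receiving all treatments (Section 3.1). Log-scale within-subject variance: σw² = ln(1 + 0.24²) = 0.0560, so σw = 0.2366. Residual df with complete data: (12 − 1)(3 − 1) = 22. Between-subject CV: assumed, 10% to 60%, with σb² = ln(1 + CV²).

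**The plan's own figure.** Section 11.4 gives limits of 1.58 to 2.53 with 80% probability at a ratio of 2. The normal approximation 2 × exp[±(1.645 + 0.842) × 0.2366 × √(2/12)] gives 1.57 to 2.54, with a probability of about 0.79 for the stated limits. This is close enough to accept σw as the planning value. The calculation concerns the ratio and contains no between-subject term.

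**The ratio.** Its standard error is σw√(2/n), whether subject is fixed or random, when data are complete. For an observed ratio of 2 the 90% CI is 1.69 to 2.36 either way. In simulation the ratio CI from the planned ANOVA covered 0.899 to 0.901.

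**The treatment mean as planned.** SE = σw/√n = 0.2366/√12 = 0.068. The log half-width is 2.074 × 0.0683 = 0.142, so the interval is the geometric mean × 0.87 to 1.15 for any σb.

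**The treatment mean as a population quantity.** The sampling variance is (σb² + σw²)/n. The planned t statistic is therefore too large by k = √(1 + σb²/σw²), and coverage is P(|t22| < 2.074/k). The alternative in the last column is a t interval with 11 df from the treatment's own log SD, exp[±2.201 × √((σb² + σw²)/12)].

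| Assumed between-subject CV | k | Coverage of planned 95% CI, n = 12 | n = 14 (26 df) | Per-treatment t interval, n = 12 |
|---|---|---|---|---|
| 10% | 1.09 | 93.1% | 93.1% | × 0.85–1.18 |
| 20% | 1.30 | 87.4% | 87.3% | × 0.82–1.22 |
| 30% | 1.59 | 79.3% | 79.2% | × 0.79–1.27 |
| 40% | 1.91 | 71.1% | 70.8% | × 0.75–1.33 |
| 50% | 2.23 | 63.7% | 63.4% | × 0.71–1.40 |
| 60% | 2.55 | 57.6% | 57.3% | × 0.68–1.47 |

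Simulation of 100,000 trials per setting at n = 12 gave 92.9%, 87.3%, 79.4%, 71.1%, 63.6% and 57.7% for the planned interval, and 94.9% to 95.1% for the per-treatment t interval.

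**Missing periods.** With 14 subjects, 2 of them lacking Period 3 (40,000 trials), the planned Period 3 interval covered 88.6%, 74.4% and 61.9% at between-subject CVs of 20%, 40% and 60%. The per-treatment t interval covered 94.8% to 94.9%.

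**The case against.** The strongest reply is that the protocol never says these intervals are for a population mean. Read as conditional on the subjects studied, they are valid. The sample is healthy volunteers at one unit, while the intended patients have CKD or heart failure, so neither interval measures uncertainty about exposure in those patients. The size of the shortfall rests on an assumed CV, and at 10% it is trivial. Descriptive statistics for the PK parameters are planned, and sponsor reporting standards not reproduced in the protocol may show the spread between subjects.

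Most of this limits the importance rather than removing the point. The conditional reading is possible, but an unlabelled 95% CI on a geometric mean invites the population reading. Descriptive statistics show spread without correcting the interval. The geometric mean and gSD plots in Section 11.2.6 are of concentrations over time, not of Cmax or AUC. The standards cited there are not said to govern the model-based intervals.

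One objection to the remedy also stands: a separately computed geometric mean can differ from the least-squares mean behind the ratio when periods are missing. That can happen here, because parameters are derived only where the data allow ("Where possible, the following PK parameters will be determined for verinurad") and single periods may be excluded ("Where the pre-dose concentration for an analyte is > 5% of Cmax in a specific PK sampling period").

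**Conclusion.** The concern holds and is minor. For any between-subject variance above zero, the 95% CIs produced by the plan as written are too narrow for a population geometric mean. That direction is certain. The size is not: for verinurad, coverage runs from 93% to 58% at n = 12 across the assumed between-subject CVs of 10% to 60%. These figures rest on the stated 24% intra-subject CV, equal variances across treatments and complete data. For M1, M8, allopurinol and oxypurinol the documents give neither CV, so only the direction can be stated. The primary ratios and their 90% CIs need no change.

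**What to change.** Leave the ANOVA with fixed treatment and subject effects as it is for the ratios and 90% CIs. Add one sentence to Section 11.2.7 and the synopsis: the 95% CI for each treatment's geometric mean is computed from that treatment's own log-scale values as mean ± t(n−1) × SD/√n, then back-transformed. If the fixed-model intervals are also shown, label them as conditional on the subjects studied. Using that label alone would remove the ambiguity but would not provide a population interval.

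A supplementary random-subject model, used only for these intervals, is an alternative. It pools variance across treatments, so it is not equivalent. It should not replace the primary model: with 2 of 14 subjects lacking Period 3, it would move the rifampicin ratio by a median of 0.8%, 0.5% and 0.4% at between-subject CVs of 20%, 40% and 60%.

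The cost is one sentence of text and one short SAS step. The intervals become wider. In the same missing-period setting, the separate geometric mean differs from the least-squares mean by a median of about 1.9%, 3.1% and 4.3% (95th percentile 5.6%, 9.0% and 12.5%), so the tabulated means may not divide exactly to the tabulated ratio. A footnote giving n per treatment and explaining this is enough.

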11.2.8. Pharmacodynamics – Not Applicable

11.2.9. Pharmacogenetics – Not Applicable

11.2.10. Exploratory Data

Results from exploratory data will not form part of the CSR and will not be included in the tables, figures or listings of this study.

11.3. Protocol Deviations

Protocol deviations are considered any deviation from the CSP relating to a subject, and include the following:

- Inclusion/exclusion criteria deviations
- Dosing deviations (eg, incorrect treatment received, subject was not fasted as per the protocol requirements prior to and after dosing)
- Time window deviations for safety and/or PK assessments
- Subjects receiving prohibited concomitant medications
- Other procedural and study conduct deviations recorded by the Clinical Unit on a protocol deviation log

The criteria for the assessment and reporting of protocol deviations will be stipulated in a separate study specific protocol deviation specification document. This will include a WAD which stipulates tolerance windows for safety and PK assessments. Measurements performed within these tolerance windows will not be considered as protocol deviations and will not be reported.

All protocol deviations will be discussed at the data review meeting prior to database hard lock in order to define the analysis sets for the study.

Protocol deviations (missing assessments/visits) related to COVID-19 will be listed separately.

Important protocol deviations will be listed by subject.

Protocol deviations will be handled in accordance with Parexel SOPs.

For handling of protocol amendments, see Section 8.6.

11.4. Determination of Sample Size

The number of subjects is based on the desire to gain adequate information on the primary endpoints while exposing as few subjects as possible to study procedures. Interpretation of the results will be based on the size of the treatment ratio and associated 90% CI. It is estimated that 12 subjects will provide a CI within 1.58 to 2.53 with a probability of 80% if the calculated treatment ratio is 2. This is based on an intra-subject CV of 24% for verinurad.

A total of 14 healthy subjects will be enrolled to ensure at least 12 evaluable subjects at the end of the last treatment period.

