Adverse events will be summarised by PT and SOC using MedDRA vocabulary. Furthermore, listings of SAEs and adverse events that led to withdrawal will be made and the number of subjects who had any AE, SAEs, AEs that led to withdrawal, and AEs with severe intensity will be summarised. Adverse events that occur before dosing will be reported separately. Tabulations and listings of data for vital signs, clinical laboratory tests and ECGs (listings only) will be presented. Any new or aggravated clinically relevant abnormal medical physical examination finding compared to the baseline assessment will be reported as an AE. Data will be summarised for the observed values at each scheduled assessment, together with the corresponding changes from the baseline when baseline is defined.

Inferential Analysis of Pharmacokinetic Data:

The pharmacokinetic parameters (Cmax AUCinf and AUClast) of verinurad, M1, M8, allopurinol and oxypurinol will be analysed using an analysis of variance model following a natural logarithmic transformation, with fixed effects for treatment and subject. Least-squares geometric means, 2-sided 95% confidence intervals, ratios of geometric means together with 2-sided 90% confidence intervals of test treatment (verinurad+allopurinol+cyclosporine or verinurad+allopurinol+rifampicin), and reference treatment (verinurad+allopurinol) will be estimated and presented. Descriptive statistics will be presented for PK concentration-time data and PK parameters for verinurad, M1, M8, allopurinol and oxypurinol.

Presentation and Analysis of Exploratory Data:

Results from exploratory data will not form part of the CSR and will not be included in the tables, figures or listings of this study.

Sample Size Determination

The number of subjects is based on the desire to gain adequate information on the primary endpoints while exposing as few subjects as possible to study procedures. Interpretation of the results will be based on the size of the treatment ratio and associated 90% CI. It is estimated

that 12 subjects will provide a CI within 1.58 to 2.53 with a probability of 80% if the calculated treatment ratio is 2. This is based on an intra-subject CV of 24% for verinurad.

TABLE OF CONTENTS

PROTOC	COL SYNOPSIS	2
TABLE (OF CONTENTS	7
List of Ta	ıbles	11
List of Fig	gures	11
List of Ap	ppendices	11
LIST OF	ABBREVIATIONS AND DEFINITION OF TERMS	12
INVESTI	GATORS AND STUDY ADMINISTRATIVE STRUCTURE	16
1.	INTRODUCTION	19
1.1.	Background	19

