11.2. Methods of Statistical Analyses

11.2.1. General Principles

The statistical methodology below describes the statistical analysis as it is foreseen when the study is being planned.

If circumstances should arise during the study rendering the analysis inappropriate, or if in the meantime improved methods of analysis should come to light, different analyses may be performed. A separate SAP will not be written for the study. Any deviations from the statistical methodology defined in this protocol, reasons for such deviations and all alternative/additional statistical analyses that may be performed will be described in the CSR. Such changes to analyses may be written into an abbreviated SAP, if appropriate. The verification and review of all statistical modeling assumptions will be documented appropriately.

All original and derived parameters as well as demographic and disposition data will be listed and described using summary statistics. All safety data (scheduled and unscheduled) will be presented in the data listings.

Demographic and baseline data will be summarised overall for all dosed subjects. Pharmacokinetic data will be summarised by treatment. Safety and tolerability data will be summarised by treatment period, if applicable.

Frequency counts (number of subjects [n] and percentages) will be made for each qualitative variable. Descriptive statistics for safety data (n, mean, SD, median, minimum and maximum) will be calculated for each quantitative variable (unless otherwise stated). Descriptive statistics will only be presented if n > 3. If no subjects have data at a given time point, then only n=0 will be presented. If n < 3, only the n, minimum, and maximum will be presented. If n=3, only the n, minimum and maximum will be presented; the other descriptive statistics will be left blank.

The following rules will apply to any repeated safety assessments occurring within each treatment period:

- If the repeated measurement of a specific parameter occurs prior to IMP administration (Day 1), then the last obtained value prior to dosing will be used in the descriptive statistics and in the calculation of changes from baseline;
- If the repeated measurement of a specific parameter occurs after IMP administration (Day 1), then the first (non-missing) value after dosing will be used in descriptive statistics and in the calculation of changes from baseline.

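### The 80% precision statement behind the sample size does not follow from its own inputs, whether 2 is the observed or the true ratio

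*Combined protocol and SAP*

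**What the plan says.** Section 11.4 states that "12 subjects will provide a CI within 1.58 to 2.53 with a probability of 80% if the calculated treatment ratio is 2". The synopsis repeats this under Sample Size Determination. On variability, Section 11.4 adds: "This is based on an intra-subject CV of 24% for verinurad". On use of the result: "Interpretation of the results will be based on the size of the treatment ratio and associated 90% CI". On enrolment: "A total of 14 healthy subjects will be enrolled to ensure at least 12 evaluable subjects" at the end of the last period.

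Section 11.2.7 plans an analysis of variance of the log-transformed parameters, "with fixed effects for treatment and subject", with two-sided 90% intervals for the ratios of geometric means. It does not say whether both comparisons (cyclosporine and rifampicin, each against verinurad+allopurinol alone) come from one model.

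Neither section gives the formula, the degrees of freedom or the unrounded CV behind the precision statement. Neither says whether the *calculated* ratio of 2 is the observed estimate or the assumed true value. Section 11.2.1 says: "A separate SAP will not be written for the study". It allows an abbreviated SAP only for changes to the planned analyses.

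**The concern.** Everything needed to check the statement is printed except the residual df, and only two values of that are plausible. A direct check does not return 80%, and the two readings of the ratio miss in opposite directions. The reader therefore cannot tell whether 12 subjects give better precision than stated or worse.

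This sentence is the only numerical support for the sample size, and the results are to be interpreted from the ratio and its 90% CI. No further planning document is foreseen in which the method would be set out.

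**Working it through.** **Inputs.** From Section 11.4: n = 12, CV = 24%, limits 1.58 and 2.53, ratio 2, probability 80%. From Sections 11.4 and 11.2.7: two-sided 90% CI on the log scale.

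**Degrees of freedom.** One model for three treatments has 36 − 1 − 11 − 2 = 22 df. Pairwise analysis has 24 − 1 − 11 − 1 = 11 df. Both are carried through.

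**Scale.**
- σ_w = √ln(1 + 0.24²) = 0.2366
- SE of the log ratio = 0.2366 × √(2/12) = 0.0966
- Log distances: ln(2/1.58) = 0.2357 and ln(2.53/2) = 0.2351
- t(0.95) = 1.796 (11 df) or 1.717 (22 df)

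**Reading 1: 2 is the observed ratio.** The interval is centred on 2, so it lies inside the limits when its half-width is at most 0.2351. Then P = Pr{χ²(df) ≤ df × [0.2351/(t × SE)]²}.
- 11 df: Pr{χ²(11) ≤ 20.19} = 0.957
- 22 df: Pr{χ²(22) ≤ 44.17} = 0.997

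**Reading 2: 2 is the true ratio.** The estimate varies as well, and both limits must fall inside. Integrating over the chi-square distribution of the residual variance gives 0.482 (11 df) and 0.526 (22 df). With the variance treated as known, it is 0.571. Two million simulations gave 0.9572, 0.9966, 0.4823 and 0.5258 for the four cases.

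**Rounding of the CV.** Probability that the whole CI lies inside 1.58 to 2.53 at n = 12:

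| CV | Observed, 11 df | Observed, 22 df | True, 11 df | True, 22 df |
|---|---|---|---|---|
| 23.5% | 0.967 | 0.998 | 0.511 | 0.556 |
| 24.0% | 0.957 | 0.997 | 0.482 | 0.526 |
| 24.5% | 0.946 | 0.994 | 0.454 | 0.497 |

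Moving the printed limits within their own rounding as well widens the ranges to 0.939–0.970 and 0.993–0.998 (observed), and 0.439–0.526 and 0.481–0.571 (true). To reach 80%, the CV would have to be 28.3% (11 df) or 30.8% (22 df) on the observed reading, or 18.6% or 19.3% on the true reading. None rounds to 24%.

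**Where the printed limits may come from.** Suppose each limit is taken alone, with a true ratio of 2 and a normal approximation. The log distance is then (1.645 + 0.842) × SE.
- CV 24.0%: 1.573 to 2.543, which prints as 1.57 to 2.54. At the printed limits, the probability is 78.7% for the lower and 78.5% for the upper.
- CV 23.5%: 1.581 to 2.531. CV 23.6%: 1.579 to 2.533. Both print as 1.58 to 2.53.
- CV 23.7%: 1.578 to 2.536, which prints 2.54.

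A one-limit t calculation with n = 14, 13 df and CV 24% also gives 1.579 to 2.533. At the stated n = 12 and CV 24%, a t-based one-limit probability is only about 74% (11 df) or 76% (22 df). Other combinations of n, df and CV can print the same limits, so the source cannot be identified from the document.

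**Limits that do carry 80% at n = 12, CV 24%, whole 90% CI.**

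| Meaning of ratio 2 | df | Log half-width | Limits |
|---|---|---|---|
| Observed | 22 | 0.1848 | 1.66 to 2.41 |
| Observed | 11 | 0.2001 | 1.64 to 2.44 |
| True | 22 | 0.2919 | 1.49 to 2.68 |
| True | 11 | 0.3021 | 1.48 to 2.71 |

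**The case against.** There are three fair points on the other side.

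First, *calculated* most naturally means observed. On that reading the sentence understates the precision, and 12 subjects are more than enough. This stands as the likelier reading of the word, but the plan does not define it. The other reading overstates the probability by 27 to 32 points (80 − 52.6 and 80 − 48.2).

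Second, a common one-limit formula with a normal approximation gives the printed limits at a CV of 23.5% or 23.6%, either of which prints as 24%. The fault may then be loose wording and not a wrong number. That is plausible, but it does not rescue the sentence. A claim to "provide a CI within 1.58 to 2.53" needs both limits inside, and the one-limit formula gives the chance for each limit separately. Under its own assumption that 2 is the true ratio, the chance for the whole interval is about 50%.

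Third, little depends on the figure. There is no hypothesis test, Section 11.4 also rests n on exposing few subjects, and the reported interval is unaffected. This is correct and limits the weight of the point to a documentation correction.

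**Conclusion.** The statement is wrong as written. With n = 12, CV 24% and a two-sided 90% CI, the whole interval lies inside 1.58 to 2.53 with probability 95.7% to 99.7% if 2 is the observed ratio, and 48.2% to 52.6% if it is the true ratio. Each range covers 11 and 22 df. Neither is near 80%, and rounding of the CV or of the limits does not change that.

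The result assumes a log-normal model with a common within-subject variance, complete data on 12 subjects, and a CV that is 24% after rounding. It does not show that the precision is inadequate or that the number of subjects should change.

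**What to change.** In Section 11.4 and the synopsis, restate the sentence so that limits, probability, n and meaning agree. Give the formula, the residual df and the unrounded CV. Say whether 2 is the observed or the true ratio, and whether the whole interval or each limit separately is meant. The sponsor should choose the reading.

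- **Observed ratio, whole interval:** with 12 evaluable subjects, a CV of 24% and an observed ratio of 2, the 90% CI lies within 1.66 to 2.41 with 80% probability (22 df; 1.64 to 2.44 with 11 df).
- **True ratio, whole interval:** replace the limits by 1.49 to 2.68 (22 df) or 1.48 to 2.71 (11 df).
- **One-limit calculation intended:** say that each limit separately, not the whole interval, meets its bound with about 80% probability, and name the n and method used.

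State in Section 11.2.7 whether both comparisons come from one model, since that settles the df. Keep 14 enrolled for 12 evaluable.

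The cost is one sentence in two places and a clarifying clause. The number of subjects, the planned analysis and the conduct do not change.
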